#### 4 Statistical Evaluation

The measured data at 'screening and baseline' visit will be used as baseline value. No imputation of missing baseline values will be applied.

The following visit notation will be used for table, listing, and graph presentation:

Notation used in the database specification/ paper case report form	Notation used for table, listing and graph presentation and in the SAP
Screening and Baseline	Baseline
Day of Surgery (Day 0)	Surgery (Day 0)
Post-Operative One Month FU (30 +/- 7 days)	Month 1
Post-Operative 3 Month FU (90 +/- 30 days)	Month 3
Post-Operative 6 Month FU (180 +/- 30 days)	Month 6
Post-Operative 12 Month FU (365 +/- 30 days)	Month 12
Post-Operative 18 Month FU (545 +/- 30 days)	Month 18
Post-Operative 24 Month FU (730 +/- 30 days)	Month 24
Post-Operative 30 Month FU (910 +/- 30 days)	Month 30
Post-Operative 36 Month FU (1095 +/- 30 days)	Month 36
Roll-in Visit (Re-consent)	Roll-in
Post-Operative 42 Month FU (1275 +/- 30 days)	Month 42
Post-Operative 48 Month FU (1460 +/- 30 days)	Month 48
Post-Operative 54 Month FU (1640 +/- 30 days)	Month 54
Post-Operative 60 Month FU (1825 +/- 30 days)	Month 60
Unscheduled Visit 1	UV 1
Unscheduled Visit 2	UV 2
> Unscheduled Visit 2	> UV 2
End of Study Page	EoS

Time window deviations will not be considered for statistical analyses.

If unscheduled visits (UVs) are not numbered according to the chronological order of the visit dates, the numbering of the UVs will be adapted for analysis. For example, if UV 4 was performed before UV 3 according to the visit dates, the UVs will be renumbered (UV 4 will get the number UV 3 and UV 3 will be UV 4). In the footnote of the listing with the visit data (see listing 1.1.2) subjects concerned will be described.

Values assessed during unscheduled visits will be listed but not used in summaries with exception of the primary endpoints. The information from UVs concerning hernia recurrence

and SSI will be included in the analysis of the primary endpoints, physical examination and rate of reoperation due to index hernia repair. Data which are gathered in the log pages (e.g. adverse event form, device failure/ malfunctions/ defects form, mesh infection form) contain information from UVs anyway.

All listings with information about several visits will be sorted by visit date per subject so that unscheduled visits are displayed in chronological order according to the visit dates.

In analyses where time intervals will be used, they are based on the following visit windows (calculated from date of surgery at Day 0):

Visit	Visit Window	Interval	
		Term	Days
1 month	Day 30 ± 7 days	Post OP – 1 month	0-37 days
3 month	Day 90 ± 30 days	>1 month – 3 months	38-120 days
6 month	Day 180 ± 30 days	>3 months – 6 months	121-210 days
12 month	Day 365 ± 30 days	>6 months – 12 months	211-395 days
18 month	Day 545 ± 30 days	>12 months – 18 months	396-575 days
24 month	Day 730 ± 30 days	>18 months – 24 months	576-760 days
30 month	Day 910 ± 30 days	>24 months – 30 months	761-940 days
36 month	Day 1095 ± 30 days	>30 months – 36 months	941-1125 days
42 month	Day 1275 ± 30 days	>36 months – 42 months	1126-1305 days
48 month	Day 1460 ± 30 days	>42 months – 48 months	1306-1490 days
54 month	Day 1640 ± 30 days	>48 months – 54 months	1491-1670 days
60 month	Day 1825± 30 days	>54 months – 60 months	1671 days - end of study

#### 4.1 Dispositions of Subjects and Analysis Sets

##### Disposition of subjects and analysis sets

Subjects per analysis sets, per center, per applicable protocol version and per visit, violation of inclusion and exclusion criteria (incl. intraoperative in-/ exclusion criteria), and the status at end of study (incl. reason for early termination) will be shown. If there are subjects that changed the study center during the study, they will be analyzed with the site where the surgery at Day 0 took place.

#### 4.2 Demographics and Other Covariates

##### Demographic data

Demographic data (age, gender, ethnicity, race, body height, body weight at baseline, body mass index (BMI)) at baseline will be tabulated.

##### Medical history

The proportion of subjects with hypertension, diabetes, immunosuppression, renal disease, cardiovascular disease, history of myocardial infarction, history of stroke, lung disease, cancer history, chemotherapy within last 12 months, pre-operative use of chronic corticosteroids, prior abdominal incisions, abdominal aortic aneurysm, history of post surgical infections, malnutrition, connective tissue disorder, alcohol abuse, cigarette smoking, drug abuse or other significant medical history will be tabulated (including frequencies of

specifications where available). Subjects with prior abdominal incisions will be listed separately including location and reason of prior abdominal incisions. From that listing a medical expert of the sponsor will determine the number of prior abdominal incisions per subject. The frequencies for the number of prior abdominal incisions will be added to the medical history table.

#### Pre-operative diagnoses and hernia assessment

Pre-operative diagnosis, mesh used for repair in case of recurrence, previous component separation technique if mesh was used, the location of hernia, size of hernia, intake of prescription or over the counter (OTC) medications for treatment of pain and the pre-study conditions of the subject will be descriptively summarized. The pre-study conditions (high risk criteria) will be presented as documented in the eCRF, where multiple entries per subject are possible, and broken down by each high risk criteria.

For sites without or subjects enrolled before approval to protocol version 2.0 (where only first time recurrent repairs are allowed and not multiply-recurrent repairs), when the index repair is a first time recurrence, the question 'if hernia recurrence, specify' receives the value 1 (= number of recurrence) and primary repairs receive the value 0. For subjects with greater than the per protocol (version before 2.0) allowed number of hernia recurrences (documented as 'other' pre-operative diagnosis with a specification on the protocol deviation form), the type (recurrent incisional or ventral hernia) and the number of hernia recurrences are incorporated into the 'pre-operative diagnosis' and 'if hernia recurrence, specify' variables. These composite variables are used throughout the analyses (see also subgroup analysis in section 3.4 above).

### **4.3 Surgery**

#### Surgical diagnoses and hernia assessment

Frequency tables for administration of prophylactic antibiotics (yes/no), surgical procedure (retro-rectus with CST/ retro-rectus without CST/ onlay placement with CST/ onlay placement without CST/ other), component separation technique (CST) performed (Ramirez, open technique/ posterior technique/ endoscopic, minimally invasive technique/ open or endoscopic technique + combinations), technique (without CST) performed (Rives-Stoppa/ open perforator preserving/ other + combinations), swiss cheese configuration (multiple discreet hernias) (yes/no) and for any reportable adverse events (yes/no) will be presented. Defect length (cm) and defect width (cm) will be summarized descriptively. Concomitant procedures will be tabulated as well.

#### Phasix™ Mesh device implant

Frequency tables for size of mesh used (7.6 cm round/ 10.2 cm x 15.2 cm/ 15.2 cm x 20.3 cm/ 20.3 cm x 25.4 cm/ 25.4 cm x 30.5 cm), method of perimeter fixation (mechanical/ suture), if suture fixation, device type (absorbable monofilament / non-absorbable monofilament/ absorbable multifilament/ non-absorbable multifilament), if recurrent, was mesh explant necessary (yes/no), wound closed (yes/no), method of closure (fascia closed/ hernia sac closed/ other), was fascia re-approximated (yes/no) and was skin fully closed (yes/no) will be presented. The number of fixation points will be summarized descriptively.

The ratio of mesh size to defect size will be calculated as mesh size ( $[\frac{1}{2} \text{ length} \times \frac{1}{2} \text{ width}] \times \pi$  in  $\text{cm}^2$ , calculation is based on the area of an ellipse) divided by the defect size ( $[\frac{1}{2} \text{ defect}$

length x  $\frac{1}{2}$  defect width] x pi in cm^2, calculation is based on the area of an ellipse). Summary statistics will be presented for the ratio of mesh size to defect size.

#### Surgical drains

A frequency table will show if a drain was placed (yes/no) and the number of drains (0/ 1/ 2/ ...). The placement, location and tube duration will be tabulated by drain number.

#### 4.4 Analysis of Primary and Secondary Variables

No formal hypothesis will be stated and statistically tested. All primary and secondary variables will be analyzed using descriptive methods. Any statistical testing, if performed, will be considered exploratory and will be based on a two-sided 5% significance level. No adjustment for multiple testing will be done. The primary and secondary variables will additionally be analyzed using the PP set (including the subgroup analyses by gender but no further subgroup analyses).

Changes from baseline will be calculated as follows:

Absolute change = post-baseline/ post procedure result – baseline result

In the following the details on the specification, definition, or calculation of the primary and secondary variables will be given.

##### 4.4.1 Analysis of Primary Variables

###### Hernia recurrence rate

Hernia recurrence rates will be assessed by physical examination at each study visit through 60 months. A recurrent hernia will be defined as any hernia identified or confirmed by the investigator, during any study follow-up visit, in approximately the same position as the hernia repaired in the study procedure. Potential hernias identified via incidental magnetic resonance imaging (MRI) or computed tomography (CT) scan will be evaluated by the operating surgeon for clinical significance and confirmation of hernia recurrence.

Hernia recurrence (after surgery including UVs) is defined as follows:

- The question “Is there any evidence of hernia recurrence in the same location as the index procedure per physical exam?” is answered with “yes”

or

- the question “Is there any evidence of hernia recurrence in the same location as the index procedure by any other means?” is answered with “yes”.

If a hernia recurrence occurs, a corresponding adverse event has to be documented. The start date of the corresponding AE is used to determine the time point of hernia recurrence. The rate of hernia recurrence will be classified in time intervals (as defined in section 4 above): post OP – 1 month, > 1 month – 3 months, > 3 months – 6 months, > 6 months – 12 months, > 12 months – 18 months, > 18 months – 24 months, > 24 months – 30 months, > 30 months – 36 months, > 36 months – 42 months, > 42 months – 48 months, > 48 months – 54 months, > 54 months – 60 months. The time of a hernia recurrence is calculated as start date of the corresponding AE minus date of device placement (surgery at Day 0). In case of more than one hernia recurrence per subject in an interval, the recurrences are counted only once per interval. In case a scheduled visit was not performed but the subject had a visit afterwards, the total number of subjects will not be reduced for the concerned time interval as the subject is still in study. If no information is available that a hernia recurrence occurred until the missed visit, no hernia recurrence is assumed for that time interval. The total number of subjects per time interval will be reduced by the number of subjects discontinued in a time interval if the time interval was not completed (according to the predetermined time windows). However, if a hernia recurrence occurred in a not completed interval the subject is counted for that interval. The date of completion or discontinuation from the end of study

page or the last visit date if the subject was lost to follow up will be used to determine the study duration of each subject since surgery at Day 0. In addition to the recurrence rates per time interval, the overall hernia recurrence rate will be calculated considering the time from post OP to end of study irrespective of the individual study duration. In case of more than one hernia recurrence per subject, the recurrences are counted only once.

Exact two-sided 95% confidence intervals (CIs) for hernia recurrence = “yes” using the SAS procedure PROC FREQ with option BINOMIAL will be calculated per time interval and overall.

The hernia recurrence rates by time intervals (visit) and overall will additionally be presented by the subgroups described in section 3.4 above (for subgroup ‘gender’ with 95%-CIs and for subgroups ‘center’, ‘pre-operative diagnosis’ and ‘surgical procedure’ without 95%-CIs).

Additionally, a Kaplan-Meier analysis for time from surgery to hernia recurrence will be performed and graphically displayed. Subjects without hernia recurrence will be censored at the last date at which they were known to have no hernia recurrence (i.e. date of completion or discontinuation from the end of study page or the last visit date if the subject was lost to follow up).

The time to event (first time of hernia recurrence as defined above) will be calculated as date difference (in days) between date of surgery (Day 0) and start date of the corresponding AE when a hernia recurrence occurred first time.

Kaplan-Meier analysis (tables and curves) will also be performed for the subgroups defined in section 3.4 above. Median time will be compared between the male and female subjects using the log-rank test. If the sample size is too low to perform an adequate valid log-rank test, the test results will not be presented.

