# **3 STUDY ENDPOINTS**

There are two primary endpoints, hernia recurrence rate and surgical site infection (SSI) rate, and six secondary endpoints:

3.1 Primary Endpoints:

1. Hernia Recurrence Rate

Hernia recurrence rates will be assessed by physical examination at each study visit through 60 months. A recurrent hernia will be defined as any hernia identified or confirmed by the investigator, during any study follow-up visit, in approximately the same position as the hernia repaired in the study procedure. Potential hernias identified via incidental magnetic resonance imaging (MRI) or computed tomography (CT) scan will be evaluated by the operating surgeon for clinical significance and confirmation of hernia recurrence.

2. Surgical Site Infections

Infections at the surgical site will be assessed by physical examination at each study visit through 60 months. If an infection is suspected, a routine culture, obtained via each site's standard protocol, should be obtained to determine cell count and type (i.e. yeast, gram positive or gram negative bacteria, or other). If genus and species of the culture are identified as part of the routine practice at the site, that information should be recorded. Classification will follow the CDC guidelines for superficial and deep surgical site infections (Appendix 3).

- 3.2 Secondary Endpoints:
  - 1. Pain Visual Analog Scale (VAS)
  - 2. Device related adverse event incidence
  - 3. Rate of reoperation due to the index hernia repair
  - 4. Quality of life assessments (Carolinas Comfort Scale® and SF-12® 12-item short form health survey)
  - 5. Surgical procedure time as measured from incision to closure (skin to skin)
  - 6. Length of stay

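### The Kaplan-Meier recurrence curve can run too high beyond Day 1825 if examination dates serve as AE start dates, which the SAP leaves undefined

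*SAP*

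**What the plan says.** Protocol 3.1 makes examination the means of finding recurrences: "Hernia recurrence rates will be assessed by physical examination at each study visit through 60 months". Protocol 6.3.3.2 makes Months 30, 42 and 54 telephone contacts unless the answers call for an office visit, so the last scheduled examination before Month 60 is at Month 48.

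SAP 4.4.1 takes the event time from the adverse event form: "The start date of the corresponding AE is used to determine the time point of hernia recurrence". Time to event is the "date difference (in days) between date of surgery (Day 0) and start date of the corresponding AE when a hernia recurrence occurred first time". For the rest, "Subjects without hernia recurrence will be censored at the last date at which they were known to have no hernia recurrence", which the SAP equates with the "date of completion or discontinuation from the end of study page or the last visit date if the subject was lost to follow up".

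SAP section 4 allows 30 days either side of Day 1825 for the Month-60 visit and adds: "Time window deviations will not be considered for statistical analyses". The last analysis interval is open-ended: "1671 days - end of study".

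The SAP text names no interval-censored method, grouping at nominal days, read-off day or point at which the curve stops. Neither document says whether the AE start date of a recurrence found on examination is the examination date or an earlier onset date.

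**The concern.** Suppose a recurrence found at the Month-60 examination is dated at that examination, and a completer is censored at his or her own. Subjects examined on Day 1800 have then left the risk set when a recurrence is recorded on Day 1845. All of them had the same examination for the same period since Month 48, but the estimator divides the late finding by only those not yet examined. The last steps of the curve become large.

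The same dating delays events at earlier times. At a nominal visit day about half of that visit's examinations are still to come, so the curve there is somewhat low.

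The Kaplan-Meier analysis is the only planned cumulative estimate of this primary endpoint that allows for length of follow-up. The interval rates are not cumulative, and the overall rate ignores individual study duration. A reader who takes the last step of the curve as the five-year recurrence could be misled.

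A second effect runs the other way. SAP section 5 says that no separate early-termination visit takes place, so a discontinuation date can fall after the last examination. SAP 4.4.1 still treats it as a date on which the subject was known to be recurrence-free.

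**Working it through.** The documents give no expected recurrence rate, dropout rate or Kaplan-Meier figure, so there is nothing to reproduce. All rates below are assumptions.

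**1. Window.** 1825 - 30 = 1795 and 1825 + 30 = 1855.

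**2. Analytic check.** Assume 20% true recurrence at 60 months, a constant hazard, and 80 subjects without a recorded recurrence who are examined in random order in the Month-60 window. Events are dated at the examination.

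- Annual hazard: -ln(0.80)/5 = 0.0446.
- Probability that the Month-60 examination shows a recurrence new since Month 48: p = 1 - exp(-0.0446) = 0.0436.
- Survival to Month 48: exp(-4 × 0.0446) = 0.8365.
- Correct grouped result: 1 - 0.8365 × (1 - 0.0436) = 20.0%.
- Planned curve at the end of the window: the factor (1 - p) is replaced by the product of (1 - p/k) over k = 1 to 80, which is 0.8039. Recurrence = 1 - 0.8365 × 0.8039 = 32.8%.
- Planned curve at Day 1825, with half examined: the product over k = 41 to 80 is 0.9704. Recurrence = 1 - 0.8365 × 0.9704 = 18.8%.

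For truths of 10% and 30% the same formulas give 17.2% and 46.8% at the end, and 9.4% and 28.3% at Day 1825.

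**3. Simulation.** 120 subjects, 1500 runs, SAP visit windows, examinations at every visit except Months 30, 42 and 54, 20% dropout, and uniform visit timing within windows. The end of the curve is Day 1855.

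| True 60-month recurrence | Exam dates: end, mean (median) | Exam dates: Day 1825 | Half dated at onset: end | All dated at onset: end | Nominal visit times |
|---|---|---|---|---|---|
| 10% | 16.7% (13.0%) | 9.5% | 13.5% | 10.0% | 10.0% |
| 20% | 32.1% (27.6%) | 18.9% | 26.4% | 20.1% | 19.9% |
| 30% | 45.5% (40.9%) | 28.4% | 38.4% | 30.3% | 29.9% |

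With examination dates the end of the curve lies above the truth in 71%, 83% and 88% of runs, and it reaches 100% in 1-5% of runs. A second simulation, with 115 subjects, gave end-of-curve means of 17%, 34% and 47% (medians 13%, 28%, 41%). At Day 1095 it gave 10.6%, against a true 36-month value of 1 - 0.80^(3/5) = 12.5%.

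**4. Sensitivity** (truth 20%, examination dates; end of curve / Day 1825):

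- visit times clustered around the nominal day: 32.6% / 19.0%
- 60% joining the extension, 30% dropout: 30.9% / 20.0%
- 95 subjects: 31.4% / 18.9%
- half of recurrences found at the telephone visits: 29.4% / 19.3%

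**5. Not run.** The interval-censored estimator and the size of the discontinuation-date effect were not computed.

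**The case against.** - **The premise is not in the documents.** Nothing says that the AE start date is the examination date, and Protocol section 8 speaks of AE onset. With true onset dates the tail bias disappears. This stands, and it makes the point conditional. But the true onset of a hernia first felt on examination is usually unknown, and dating half of the events at onset still gives 26.4% for a truth of 20%.
- **The 60-month value is not inflated.** A reader might infer that the plan overstates recurrence at 60 months. It does not: Month 60 is Day 1825, where the curve is about one point low. The excess lies beyond that day, and the SAP names no read-off at the end of the curve. This stands.
- **The analysis is supplementary.** There is no hypothesis and no decision rule, and the interval and overall rates with exact confidence intervals do not have this tail problem. This stands and limits the weight of the point.
- **Detection is less regular than modelled.** Unscheduled visits, the roll-in examination, symptom-prompted visits and incidental imaging also find recurrences. Completers are censored at the completion date on the end of study page, which need not be the examination day. Both can reduce the effect. For telephone-visit detection the reduction was small (29.4% instead of 32.1%).
- **Table layouts are in SAP Appendix A,** which is not among the documents. Numbers at risk or landmark times may be specified there.

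**Conclusion.** The concern holds in conditional form. SAP 4.4.1 leaves the AE start date of a recurrence found on examination undefined, and the tail of the curve depends on it. With dates at or near the examination, and completion dates close to the Month-60 examination, the curve can overstate recurrence beyond Day 1825. For an assumed truth of 20% the end-of-curve mean is about 32-34% and the median about 28%. The mean is pulled up by a few runs with very large last steps, so the median better describes a typical trial. Read at nominal days, the same curve is low: by about two points at Day 1095 and about one point at Day 1825. With onset dates there is no material tail bias.

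The documents do not support the stronger reading that the planned analysis overstates 60-month recurrence outright. The sizes rest on assumed hazard, dropout and visit scatter. The censoring of discontinued subjects after their last examination is a separate, unquantified weakness in the opposite direction. The change is worth making because it concerns a primary endpoint and uses data already collected.

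**What to change.** In SAP 4.4.1:

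1. Base the cumulative recurrence estimate on one of two methods: an interval-censored (Turnbull) analysis between the last negative and first positive assessment, or a Kaplan-Meier analysis grouped at nominal visit times, with events placed before censorings at ties.
2. In the grouped version, assign recurrences found at unscheduled visits or by imaging to the SAP section 4 interval in which they were found.
3. Censor at the last completed assessment for recurrence, not at the discontinuation date, and state whether a telephone contact without an examination counts as one.
4. Read the 60-month estimate at the nominal Month-60 time with its 95% confidence interval and number at risk. Do not interpret the curve beyond that time.
5. Keep the AE-start-date curve as supportive, and state what the AE start date means for a recurrence found on examination.

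The cost is SAP wording and two derived times (event and censoring). The downside is that the grouped curve steps only at visits.

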			
for subgroup analysis by site is defined because the enrollment period had finished.
 
 
The two primary endpoints (hernia recurrence rate and the surgical site infection rate) as well as the rate of reoperations due to index hernia repair are analyzed by disjointed time intervals (Post OP – 1 month/ > 1 month – 3 months/ > 3 months – 6 months/ > 6 months – 12 months/ > 12 months – 18 months/ > 18 months – 24 months/ > 24 months – 30 months/ > 30 months – 36 months) instead of cumulative time intervals post device placement (Until Month 1/ Until Month 3/ Until Month 6/ Until Month 12/ Until Month 18/ Until Month 24/ Until Month 30/ Until Month 36).
 
Some specifications were added.
 

3.0	[name]	21SEP2017	
 
Based on sponsor’s review of TLGs (“dry run”), changes in the SAP 2.0 were requested: 
 
- In the presentation of frequency tables special missing values, as ‘not done’, ‘unknown’, ‘not applicable’, ‘not documented’, should not be merged to the value ‘missing’ but be presented separately.
 
- Some tables should be stratified by gender and visit instead of by visit and gender.
 
- Some listings should be reduced to the “yes”-cases (e.g. SSI=yes).
 
- Some footnotes to tables/listings were added/ modified and variables to listings were added in Appendix A.
 
- Specifications added, typos corrected.
 
- Surgical Procedure time should be calculated in minutes instead of hours.
 
 
 
[name] signs the SAP instead of [name].
 
Criterion (Index hernia repair/ Phasix™ Mesh cut through or a piece of the Phasix™ Mesh removed during a surgery) for exclusion from PP set added.
 
For the hernia recurrence rate, SSI rate and rate of reoperation due to the index hernia repair an overall rate is added to the rates per time interval.
 

4.0	[name]	07AUG2018	
 
New protocol version 4.0 of October 30, 2017: 24 month extension of the study. The changes are effective for sites that approve this protocol change. Sites without an approval proceed according to protocol version 3.0. Visit window for 36 month visits changed
 

Version	Author	Date	Reason for Revision

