			
from Day 1090 ± 30 days post device placement to Day 1095 ± 30 days post device placement.
 
 
• Some specifications were added.
 
• The following terminology was modified:               
 
- “Defect ratio” was changed to “Ratio of mesh size to defect size” and
 
- “Screened subjects” was changed to “Enrolled subjects”.
 
 
 

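### The hernia recurrence interval rates use denominators that depend on the outcome, keep earlier recurrers and leave 36-month completers unsettled, so they need not agree with the planned first-event Kaplan-Meier analysis

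*SAP*

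**What the plan says.** SAP 4.4.1 (Hernia recurrence rate) gives one reason to shrink an interval's denominator: "The total number of subjects per time interval will be reduced by the number of subjects discontinued in a time interval", on the condition "if the time interval was not completed (according to the predetermined time windows". It then makes an exception: "However, if a hernia recurrence occurred in a not completed interval the subject is counted for that interval".

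Repeat events are handled differently in the two displays. For the intervals: "In case of more than one hernia recurrence per subject in an interval, the recurrences are counted only once per interval". For the overall rate: "In case of more than one hernia recurrence per subject, the recurrences are counted only once". Nothing takes a subject out of later intervals after a first recurrence. The Kaplan-Meier analysis in the same section uses the first recurrence only and censors event-free subjects at the end of their follow-up.

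Some subjects finish at 36 months. Protocol 4.0 added 24 months to reach 60, and the SAP revision history (version 4.0) says: "Sites without an approval proceed according to protocol version 3.0". It records that the 36-month window changed "from Day 1090 ± 30 days post device placement to Day 1095 ± 30 days post device placement". In the interval table of SAP section 4, the 30-36 month interval is Days 941-1125. Only the last interval is open-ended ("1671 days - end of study").

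The SSI rate is analyzed in the same way.

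**The concern.** Three features separate these rates from first-recurrence risk among subjects at risk.

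1. Of two subjects who leave in the same interval, the one event-free in it is dropped and the one who recurred in it is kept. This pushes the rate up.
2. Subjects who have already recurred stay in later denominators although they can no longer have a first recurrence. This pushes the rate down.
3. The SAP does not say whether a subject finishing at 36 months under protocol 3.0 has completed an interval that runs to Day 1125, or that this subject leaves the denominators after Month 36.

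The interval rates with exact confidence intervals are a main display of a primary endpoint. They will stand beside Kaplan-Meier results built on a different risk set, with no label to tell the reader so. On the third feature, two competent programmers could produce different denominators from the same text.

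**Working it through.** The plan gives no recurrence, loss or 36-month-ending rate, so it has no figure to reproduce.

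**Inputs from the documents.** N = 120 (Protocol 5.1, 7.2). The 30-36 month interval is Days 941-1125, which is 185 days; the last interval starts on Day 1671 (SAP section 4). The protocol 3.0 window is Day 1090 ± 30, so Days 1060-1120.

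**Assumptions.** Constant recurrence hazard; 60-month risk 20% (range 10% to 30%); 5% loss per year; at most one recurrence per subject; 0% to 50% of subjects ending at 36 months.

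**Step 1: true interval risk.** λ = −ln(0.80)/1825 = 0.0001223 per day. p = 1 − exp(−185λ) = 2.24%.

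**Step 2: non-completer rule alone.** Let a share d leave evenly over the interval. The rate is about p(1 − d/2)/(1 − d + dp/2).
- d = 2.5%: 0.02237 × 0.9875/0.97528 = 2.26% (about +1% relative)
- d = 5%: 2.29%
- d = 10%: 2.36% (about +5%)

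A loss of 5% per year is close to d = 2.5% per half-year interval, so the low end applies under the main assumption.

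**Step 3: retained recurrers.** The relative shortfall is the share already recurred when the interval starts.

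| 60-month risk | 1 − exp(−941λ) | 1 − exp(−1671λ) | Last interval if all recurrers before Day 1095 are barred: 1 − exp(−576λ) |
|---|---|---|---|
| 10% | 5.3% | 9.2% | 3.3% |
| 20% | 10.9% | 18.5% | 6.8% |
| 30% | 16.8% | 27.9% | 10.6% |

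The last column is an extreme case: the extension criterion (Protocol 5.3.2) excludes surgery through the index site, not recurrence as such. If earlier recurrers can recur again at half the first-event hazard, the 10.9% shortfall falls to about 5%. At the same hazard it is zero.

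**Step 4: 36-month completers in Days 941-1125.** An in-window protocol 3.0 completer is seen by Day 1120, five days before the interval closes. In 20,000 simulated trials at 20% risk, with 36-month ends uniform on Days 1060-1120:

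| Share ending at 36 months | Completers kept | Dropped unless they recurred | Ratio |
|---|---|---|---|
| 0% | 2.02% | 2.02% | 1.00 |
| 10% | 1.98% | 2.20% | 1.11 |
| 25% | 1.93% | 2.57% | 1.33 |
| 50% | 1.82% | 3.59% | 1.97 |

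At 50% the mean denominators are about 103 and 52. The first row combines steps 2 and 3: the two effects partly cancel, leaving 2.02% against a true 2.24%.

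**Step 5: after Month 36.** In a smaller simulation with 50% ending at 36 months, the 36-42 month rate is 1.0% (denominator about 102) if completers stay in and 2.0% (about 50) if they are removed.

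**Step 6: SSI.** Protocol Appendix 3 limits SSI to 30 days, or to one year for deep infection with an implant, so the late-interval effects hardly apply. In Days 38-395 the rate is lowered by the share already infected: 5% to 15% relative if 5% to 15% were infected earlier (assumed).

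**The case against.** The strongest reply is that a first-event analysis is already planned. The study is descriptive with no hypothesis (Protocol 7.1, SAP 4.4), separate intervals were a deliberate choice (SAP revision history, version 2.0), and two different summaries may differ without either being wrong. Because the SAP provides for repeat recurrences, an any-event proportion over everyone in the study is a legitimate quantity. The non-completer effect is tiny. The natural reading of step 4 is to keep the completer: the reduction names discontinued subjects, and Protocol section 8 separates finishing the study from leaving it early. Sampling error is also far larger than most of these shifts: the exact 95% interval for 2/103 is 0.2% to 6.8%.

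Much of this stands, and it limits the size of the point. It does not remove it. The Kaplan-Meier analysis does not correct the tabulated rates, and the SAP does not label them as any-event proportions. The time-window condition, together with study duration measured to the date of either finishing or discontinuing, leaves room to drop the completer.

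A reader might infer that the primary result could be wrong by a factor of two. That needs both an assumed 50% ending at 36 months and the less favoured reading. A reader might also infer that the exact intervals are invalid, or that the SAP presents these rates as first-event risk. The first is not shown in general, and the SAP makes no such claim.

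**Conclusion.** The point holds as a defect of definition with a modest expected effect. The interval denominators depend on the outcome, keep earlier recurrers by silence, and do not settle the 36-month completers, so the rates need not agree with the Kaplan-Meier analysis.

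The first two effects run in opposite directions, and their net size depends on rates that the documents do not give. The retained-recurrer figures are upper values: they shrink if subjects can recur again or if recurrers do not enter the extension. The largest possible shift comes from the 36-month completers. The wording leans towards keeping them in the 30-36 month interval, and the study-duration sentence leans towards removing them afterwards, but neither is stated. The matter concerns hernia recurrence far more than SSI. It should be corrected before database lock, so that the denominator is not chosen with outcomes visible in an open-label study.

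**What to change.** For each interval, take as the risk set the subjects who are event-free and under follow-up at its start. Count first events only, and treat all exits alike whatever the outcome. One way is to report the conditional interval risk, 1 − S(end)/S(start), from the planned Kaplan-Meier or a life-table analysis.

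Use a confidence interval that does not collapse when an interval has no event, as a plain Greenwood interval does. With 85 at risk and p = 2.24%, the chance of no event is (1 − 0.0224)^85, about 15%.

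State that a subject who completes the 36-month visit under protocol 3.0 completes the 30-36 month interval and leaves all later denominators. The same sentence can cover subjects at approving sites who do not enter the extension.

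If the any-event period proportion is also kept, label it as such and say that earlier recurrers remain in its denominator. Carry the same rules to SSI.

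The cost is SAP wording and re-programming of one table family. No new data are needed and no decision rule changes.
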